6.3.5 Exploratory Endpoints

1. Procedure time (from positioning of the patient to removal of the drape from the subject's back)
2. Incidence of conversion from spinal to epidural (specific to neuraxial anesthesia)

6.4 Study Population

Subjects admitted to EM, neurology, or anesthesiology settings that require a neuraxial procedure as part of their management or work up, and that meet inclusion and exclusion criteria will be approached by research staff for enrollment in the study. Spinal punctures in these clinical settings involve the same localization and insertion processes, through access to the spinal canal. Written informed consent will be obtained in person by the study coordinator or designee.

6.4.1 Sample Size

It is expected that approximately 120 subjects will be screened to meet a target enrollment goal of 96 subjects (48 in each group) across 3 investigational sites.

The superiority hypothesis for the number of insertion attempts with IntuiTap (μ_1) and palpation (μ_2) is:

$$H_0: \mu_1 \geq \mu_2 \text{ vs } H_1: \mu_1 < \mu_2$$

The sample size was selected based on historical information and previous clinical trial data collected with the VerTouch device. A literature survey identified eight (8) papers where the mean and standard deviation (SD) for insertions for palpation were identified^[25-32]. The definitions appear similar to the proposed endpoint. The mean attempts ranged from 1.3 to 3.3 and SD ranged from 0.0 to 6.9. A weighted average of the means and standard deviations provided an average of mean of 2.3 and SD of 2.8^[33]. Based on the spread of individual results, a mean of 2.1 and SD of 1.5 was considered a reference for the power analysis.

A sample of 81 attempts was available for the VerTouch device across several iterations of the device. Of the attempts, 90% were successes on the first attempt and the mean number of attempts was 1.1 and SD was 0.6.

In order to assess the sample size, given the truncated nature of the distribution and the planned use of a bootstrap analysis, a simulation study was performed. Random vectors were built by taking the ceiling of absolute values of a mixture for two normal distributions to build long-tailed distributions with means and standard deviations similar to those above. Analyses were done using a bootstrap analysis of the difference in means, Wilcoxon Test, T-test with unequal means, and a T-test of log-transformed data. For a sample size of 24 subjects per group, the bootstrap analysis,

Wilcoxon Test, and T-test of log-transformed data had at least 92% power while a T-test of the observed counts had 89% power.

In addition, an estimate of the secondary endpoint of first attempt success of approximately 50% was obtained in the simulation exercise for palpation. The planned sample size of 48 per group provides 90% power when compared to a first attempt success rate of 81% in the VerTouch group. Hence, the study is also expected to have adequate power for the primary analysis and the secondary endpoint of success on the first insertion.

6.4.2 Subject Recruitment

Subjects will be recruited from investigators practicing at large hospital settings from Anesthesiology, Neurology or the Emergency Departments. Those departments will be used to recruit subjects into this study.

6.4.3 Subject Screening

Following Informed Consent, subjects will be screened for eligibility. Height and weight will be recorded, and BMI calculated. Scheduled date of eligible procedure will be recorded. Relevant medical history and age will be assessed for concordance with inclusion and exclusion criteria. Subjects who do not meet eligibility criteria will be recorded as Screen Failures. At subject screening, subjects will be given a subject ID number that encodes both investigational site and subject number.

6.4.4 Prior and Concomitant Medications

There are no restrictions on prior or concomitant medications. However, concomitant prescription and over the counter (OTC) pain and anti-anxiety medications must be recorded in the source documentation and in the eCRF.

6.4.5 Inclusion Criteria

Subjects will be eligible to participate in the study if **all** of the following conditions exist:

1. Males and females aged 18 years and above, inclusive
2. Subjects scheduled for one of the following procedures:
 - Diagnostic LP (collection of CSF and/or measurement of ICP to diagnose hemorrhage or neurological infection)
 - Therapeutic LP (intrathecal injection of therapeutic agents; drainage of CSF to treat pseudotumor cerebri)

- Planned orthopedic or obstetric procedure, such as labor/induction, cesarean section, hysterectomy, or total hip/knee replacement, with neuraxial anesthesia (injection of anesthetic into spinal and/or epidural space to reduce pain during procedure)
- Epidural blood patch (use of autologous blood to close holes in the dura mater and relieve PDPH)

3. Subjects having a BMI $\leq 42\text{kg/m}^2$

6.4.6 Exclusion Criteria

Subjects will be excluded from participation in the study if **any** of the following conditions exist:

1. Patient does not provide informed consent
2. Skin or soft tissue infection near the puncture site
3. Allergy to local anesthetic
4. Uncorrected coagulopathy
5. Acute spinal cord trauma
6. History of lumbar spinal surgery
7. Prior known failed neuraxial anesthesia
8. Diagnosed scoliosis, thoracic kyphosis, lumbar lordosis, scleroderma, ankylosing spondylitis, or lumbar spinal stenosis
9. Incarcerated subjects

6.4.7 Exit / Discontinuation Criteria

Subjects will exit the study if any of the following conditions exist:

1. Subject voluntarily withdraws from the study.
2. Subject death.
3. Subject acquires any of the listed exclusion criteria.
4. Subject completes the protocol.
5. Subject's well-being, in the opinion of the Investigator, would be compromised by study continuation.

7 Study Procedures

7.1 Informed Consent

All prospective subjects for this study will be provided a consent form describing this study and providing sufficient information for subjects to make an informed decision about their participation in this study. The consent form will be submitted

with the protocol for review and approval by the IRB for the study. The formal consent of a subject, using the IRB-approved consent form, must be obtained before that subject is submitted to any study procedure. This consent form must be signed by the subject or legally acceptable surrogate, and the investigator-designated research professional obtaining the consent. A blank copy of the IRB-approved form must be kept on-site and by the Investigator.

Subjects who sign an informed consent will be considered enrolled in this study. Subjects who provide consent for participation but do not meet all study eligibility criteria will be considered screen failures.

7.2 Vulnerable Populations

As noted above adolescent subjects (18-21 years) will be eligible for participation in this study. Pregnant women will be recruited for the cohort including obstetric procedures, such as labor/induction and cesarean section, and eligible to participate in other cohorts as well.

Other recognized vulnerable populations will not be targeted for recruitment, however individual subjects within vulnerable populations may be enrolled. The Human Subject's Protections procedures employed in this protocol are sufficient to protect the rights and welfare of any subject within an eligible vulnerable population and no additional measures are necessary.

7.3 Randomization Scheme

Qualifying subjects will be randomized 1:1 via a block randomization scheme to either the tactile-imaging group (T) or the palpation group (P) within each setting (e.g. EM, neurology, or anesthesiology).

7.4 Clinical Procedures

7.4.1 Visit 1

Screening

At the screening visit the following activities and information will be collected:

- Informed Consent
- Physical Examination (height/weight)
- Eligibility Determination
- Randomization and Subject ID Assignment

- Demographics (gender, age, race, ethnicity)
- Relevant Medical History
- Concomitant Medications

At Treatment

At the time of treatment, the following activities and information will be collected:

- Concomitant Medications
- Pain and/or anti-anxiety medication(s) given for the procedure
- Provider level of training (e.g. resident, fellow, attending, PA, CRNA, NP)
- Provider number of years of in practice
- Provider experience (i.e. number of neuraxial procedures performed in the past 12 months)
- Provider specialty (i.e. emergency medicine, neurology, anesthesiology)
- Procedure setting (i.e. emergency medicine, neurology, orthopedic anesthesiology, obstetric anesthesiology)
- Type of neuraxial procedure (i.e. diagnostic LP, therapeutic LP, spinal anesthesia, epidural anesthesia, CSE, blood patch)
- Reason for Neuraxial Procedure (if not diagnostic LP or blood patch), such as:
 - Therapeutic LP: CSF drainage, intrathecal injection, other
 - Orthopedic procedure: total hip replacement, total knee replacement, other
 - Obstetric procedure: labor/induction, cesarean section, hysterectomy, tubal ligation, other

The subject will be treated with the device or control, per **Figure 6** below (see IFU for more detailed VerTouch steps)^[24]. Initial landmarking for vertebral level is performed by standard technique in both groups in order to identify a safe level when placing the drape to expose the procedure area.

Listed data will be recorded in source documentation, by a member of the study team designated as an observer, as they become available. The observer will also be responsible for counting needle insertions and redirections. Note that procedure success may be reported at different points within the treatment, depending on when spinal access can be confirmed for the particular neuraxial procedure.

[figure not shown]

Figure 6. Flowchart of Visit 1 treatment.

Post-Treatment

After the completion of the procedure, the following activities and information will be collected:

- Patient position (seated, lateral decubitus)

- Length, gauge, bevel (cutting, non-cutting), and type (straight, curved) of needle used
- VerTouch workflow followed (N/A (control group), marking, introducer placement, needle placement)
- Calculation of number of re-insertions (1 less than insertions)
- Incidence of first-insertion success (1 insertion, any number of redirections)
- Calculation of number of passes (sum of insertions and redirections)
- Incidence of first-pass success (1 pass)
- Calculation of localization, insertion, and procedure times (based on start and end times)
- Incidence of traumatic tap
- Incidence of referral to radiology
- Incidence of conversion from spinal to epidural (neuraxial anesthesia only)
- Incidence of paresthesia (neuraxial anesthesia only)
- Incidence of PDPH
- Intensity of PDPH (mild, moderate, severe)
- Incidence of unintended dural puncture (epidural anesthesia only)
- Subject Discomfort Assessment
- Provider Confidence Assessment
- Adverse Event Assessment
- Upload of data from VerTouch

Post-procedure, the subject will be monitored for adverse events, adverse device effects or other reportable observations to ensure safety, entering relevant data into the eCRF. At the conclusion of the visit, the subject will be released and considered complete. After each procedure, imaging data from VerTouch will be uploaded by the designated observer to a study portal to support investigation of any anomalous finds and/or establishment of a human image database.

7.4.2 Visit 2

Visit 2 must occur at 3 ± 2 days following Visit 1. Phone, or other appropriate follow-ups will be made at Visit 2 to assess the presence and intensity of PDPH in subjects, and assess potential adverse events. At the conclusion of Visit 2, a Subject Study Exit CRF will be completed.

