7.6 Study Timetable / Schedule of Events

Table 2. Schedule of Events

Assessment	Visit 1			Visit 2
	Screening	Treatment	Post-Treatment	Follow-up
Demographics	X			
Medical History	X			
Physical Exam (Height & Weight)	X			
Inclusion/Exclusion Criteria	X			
Informed Consent	X			
Randomization	X			
Concomitant Medications	X		X	
Procedure Completion		X		
Discomfort Assessment			X	
Provider Satisfaction Assessment			X	
PDPH				X
Adverse Event Assessment			X	X
Adverse Device Effect Assessment			X	X

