8.1 Subject Population(s) for Analysis

The study populations are defined as follows:

- Intent-to-treat population (ITT): Consists of all randomized subjects according to their randomized group.
- Per-protocol population (PP): Consists of all subjects who received their randomized treatment, did not have an inclusion or exclusion violation, had a procedure success, and did not have a major protocol deviation.

The primary analysis and all study results will be analyzed using the ITT population. The primary analysis will be repeated using the PP population.

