8.2 Statistical Methods

This section describes the planned statistical analyses for this study. A detailed Statistical Analysis Plan (SAP) will be completed and placed on file prior to enrollment. The SAP will contain a comprehensive explanation of the methodology used in the statistical analyses described below.

All CRF data will be made available in data listings or in Excel spreadsheets. Data listings will be sorted by subject and visit date, or adverse event onset date. All statistical analyses will be based on the available data. The study results will be reported in summary tables using standard descriptive statistics. Standard numeric descriptive statistics include the n (number of non-missing observations), mean, median, minimum value, and maximum value. Categorical data will be summarized using the counts and percentages based on the non-missing values.

Statistical analyses will be performed to assess the homogeneity of the study populations, evaluate the primary hypothesis, and evaluate the impact of covariates on the performance of the VerTouch device. Standard statistical tests used for

hypothesis testing are the t-test for numeric measures and the likelihood ratio chi-square test for categorical variables. For categorical variables with small cell counts (less than 5), Fisher's exact test will be used. For inferential analyses, unless otherwise indicated, a two-sided p-value of less than or equal to 0.05 will be considered statistically significant. All confidence intervals (CIs) will be two-sided 95% intervals. Note that p-values reported for tertiary and exploratory endpoints will be used for reporting but would not be used in product labeling.

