8.2.2 Primary Effectiveness Analysis

The study is designed to evaluate whether the use of the VerTouch device is able to reduce the number of insertion attempts to successfully access the spinal canal in a spinal puncture as compared to the conventional palpation technique. The primary hypothesis test will be performed by a bootstrap analysis resampling the cases in each group. The null hypothesis for the analysis is:

$$H_0: \mu_1 \geq \mu_2 \text{ vs } H_1: \mu_1 < \mu_2$$

Where μ_1 is the mean attempts in the VerTouch group and μ_2 is the mean for palpation.

This hypothesis will be evaluated using a bootstrap analysis with a one-sided 0.025 test to indicate statistical significance. The results will be presented for the difference in means and the associated 95% CI; and the ratio of the VerTouch mean divided by the palpation mean and the associated 95% CI.

The primary analysis will include the total insertions for each subject regardless of success on the final placement attempt.

The following supporting analyses will be performed:

- The primary analysis will be performed only for subjects who had a procedure success.
- If there are missing data, best- and worst-case imputation analyses will be performed. For the worst-case imputation, the highest observed value will be imputed in the VerTouch group and the lowest value in the palpation group. The best-case analysis reverses the pattern of imputations.
- A Wilcoxon rank-sum test will be used to evaluate the null hypothesis that median attempts are the same in both arms using a two-sided test with a p-value less than or equal to 0.05 considered significant.
- Homogeneity of the log-transformed count results will be assessed using an ANOVA with site, treatment, and site-treatment interaction terms. A p-value for the site-treatment interaction of less than or equal to 0.15 will be considered statistically significant for this analysis. The n, mean, and SD of values by study site will be provided by treatment group.
- The observed attempts will be evaluated through a t-test for unequal variances comparing the difference in the log (insertion attempts) for each group. The difference will be transformed with the exponent function to provide the ratio of the geometric mean attempts and a two-sided 95% CI for the ratio.

The following subgroups will be considered in exploratory covariate analyses:

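### Randomisation at screening can leave ITT subjects without a primary count: primary power barely moves, but losses may depend on arm and the worst-case supporting analysis is fragile

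*Protocol*

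**What the plan says.** Protocol section 7.4.1 opens its Screening block with "At the screening visit the following activities and information will be collected" and includes "Randomization and Subject ID Assignment" in the list. Table 2 (section 7.6) and the table in SAP section 6 both mark "Randomization" under Screening. Section 6.1 says only that randomisation follows consent.

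The step shared by both arms comes later, under At Treatment: "Initial landmarking for vertebral level is performed by standard technique in both groups", done when the drape is placed.

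At screening the subject has a scheduled procedure (section 6.4.5), and section 6.4.3 adds "Scheduled date of eligible procedure will be recorded". No section requires the same day or sets a maximum interval.

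On analysis, section 8.1 defines ITT as follows: "Consists of all randomized subjects according to their randomized group". It makes ITT the set for the primary analysis. Section 6.3.1 counts forward needle movements after skin puncture. Section 8.2 states "All statistical analyses will be based on the available data". Section 8.2.2 and SAP 8.3.3.3 add best- and worst-case imputation; in the worst case "the highest observed value will be imputed in the VerTouch group and the lowest value in the palpation group". Section 7.8 does not anticipate withdrawals. The SAP lists mITT as an abbreviation but defines no such population in its section 7.

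**The concern.** Between screening and skin puncture a subject can withdraw or acquire an exclusion criterion (both are exit reasons in section 6.4.7), or the procedure can be cancelled or changed. Section 9.2.1 itself mentions labour cases in which the chance to give anaesthesia could be missed. Such a subject is ITT by definition but has no insertion count, because there was no insertion.

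The primary test would then compare subjects who went on to be punctured. The trial is open-label, so subject and provider may know the arm before anyone commits to a needle, and the reasons for not starting could differ by arm. The imputation rule also treats a subject who was never treated like one whose count was not recorded, and gives each an extreme value. A few such subjects could overturn that supporting analysis for reasons unrelated to the device.

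**Working it through.** **1. Inputs.** Protocol 6.4.1 gives 48 per group; palpation mean 2.1, SD 1.5; VerTouch mean 1.1, SD 0.6; first-attempt success 50% against 81%. The primary test is one-sided at 0.025. The share of randomised subjects with no procedure is not given; 0 to 20%, equal in both arms, is assumed.

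**2. The plan's own figure.** Power for first-attempt success is Φ[(Δ√n − 1.96√(2p̄q̄)) / √(p₁q₁ + p₂q₂)]. With Δ = 0.31, n = 48 and p̄ = 0.655, this is Φ[(2.148 − 1.318)/0.6355] = Φ(1.306) = 90.4%. The stated 90% reproduces. It contains no allowance for subjects without a count.

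**3. Available-data power after loss.** For the primary endpoint the standard error is √[(0.6² + 1.5²)/n] = √(2.61/n). At n = 48 it is 0.233 and the ratio is 1.0/0.233 = 4.29. At n = 38 it is 0.262 and the ratio is 3.82. Unequal-variance t-test power:

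| Assumed loss | n per arm | Primary | First-attempt success |
|---|---|---|---|
| 0% | 48 | 98.8% | 90.4% |
| 5% | 45 | 98.3% | 88.5% |
| 10% | 43 | 97.9% | 87.0% |
| 20% | 38 | 96.2% | 82.5% |

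The primary column depends on the SD of 1.5. With the weighted literature average that section 6.4.1 also reports (mean 2.3, SD 2.8), the same calculation gives 81.3% at 48 per arm and 71.3% at 38.

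**4. Worst-case imputation.** With k missing per arm, H imputed for VerTouch and 1 for palpation, the expected difference is [(48 − k) × 1.0 − k(H − 1)]/48. Each missing pair therefore costs H/48. Simulated differences under the pooled reading were 0.99, 0.84, 0.69 and 0.54 for k = 0 to 3, a drop of 0.15 each, so H is about 0.15 × 48 = 7.2.

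Chance that the worst-case result is significant:

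| k per arm | Pooled maximum, model A | Pooled maximum, model B | Maximum within VerTouch, model A |
|---|---|---|---|
| 0 | 98% | 99% | 98–99% |
| 1 | 92–93% | 91% | 95% |
| 2 | 72–73% | 66% | 88% |
| 3 | 42% | 31% | 83% |

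Model A uses shifted negative binomial counts with the planning means and SDs and the unequal-variance t-test in place of the bootstrap. Model B uses the bootstrap, palpation counts from a normal mixture (mean about 2.1, SD about 1.5) and VerTouch counts with 90% at one insertion (mean about 1.16, SD 0.59). Three per arm is 3/48 = 6.25%. The text does not say whether the highest value is taken within the arm or overall, hence two readings.

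**5. Direction of an arm-dependent loss.** Under model A, if the three hardest palpation cases never start, the difference falls from 0.99 to 0.74 and power is about 96%. That works against the device. Loss of hard cases from the VerTouch arm would work the other way. The documents do not say which is more likely.

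**The case against.** The best defence has five parts.

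- **Timing.** Screening, treatment and post-treatment are all Visit 1. The protocol times follow-up at 3 ± 2 days from Visit 1 and the SAP from treatment, and these coincide only if both fall on one day. This stands: a reader might infer randomisation days ahead, but the documents only leave that open. The point does not need it, since a same-day cancellation has the same effect.
- **Frequency.** A reader might take the radiology referral rate above 47% in section 2.1 as the likely loss. It is background on challenging cases, not a rate of referral between randomisation and puncture; in this trial referral is a recorded outcome (section 6.3.3).
- **The primary test.** A reader might infer an underpowered primary test or a route to false superiority. Neither is shown. Power moves little under the planning values, and the one worked example of selective loss penalises the device.
- **The imputation.** It is a supporting bound, meant to be extreme, with no success criterion attached. The pooled-or-within-arm ambiguity is a fault of its wording, not of randomisation timing. Both are true. The bound is nevertheless the plan's only analysis aimed at missing counts, and it informs little if a handful of untreated subjects decides it.
- **Existing provisions.** The plan is not silent: SAP 8.3.1 reports how many complete the procedure and the reasons for discontinuation. That discloses the losses but does not prevent them, and it does not separate a subject never punctured from a count not recorded.

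Figures 5 and 6 were not available in the text and could show a later randomisation point; the text and both schedules agree on screening.

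**Conclusion.** The point holds in a limited form. Randomisation at screening is explicit, and an ITT subject with no primary value follows directly from the ITT and endpoint definitions. The available-data analysis then excludes that subject after the arm can be known.

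The cost in primary power is small: above about 96% at 20% loss, given the planning means and SDs. The remaining concerns are selection that may depend on arm, in a direction the documents do not settle, and a worst-case analysis whose chance of significance drops from about 98–99% to 31–42% (pooled maximum) or about 83% (within VerTouch) with three missing per arm. These figures rest on an assumed number of missing subjects and assumed count distributions. The change is worth making because it is cheap and removes most such losses at source.

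**What to change.** - **Move randomisation.** In protocol 7.4.1, Table 2 and the SAP section 6 table, place it on the day of the procedure: after consent, eligibility and baseline data, once the provider and team are ready to begin, and immediately before the patient is positioned. Subject ID assignment can stay at screening, as section 6.4.3 has it.
- **Why before positioning and not after landmarking.** Procedure time starts at positioning (section 6.3.5). Later allocation would put device dispensing and sterile assembly inside the timed interval for VerTouch only. Section 3.2 also has the workflow chosen before the procedure begins.
- **Amend sections 6.4.3 and 7.1.** They limit screen failures to subjects who fail eligibility. Add a category, not randomised, for eligible subjects whose procedure is cancelled or redirected before allocation.
- **Report the remainder.** In SAP 8.3.1, list randomised but never punctured subjects by arm and reason.

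The cost is wording in two documents and one row in each schedule, with no added visits. The downside is a short wait before the procedure, because the VerTouch set can be prepared only after allocation.
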